There is no reason to believe that Infudopa would exhibit any additional systemic adverse reactions than those described for other levodopa/carbidopa products, as summarised in the product information for Duodopa (see Investigator's Brochure). Duodenal administration of Duodopa has, however, a high risk of device- and procedure-related adverse reactions, such as postoperative wound infection, excessive granulation tissue, and incision site erythema, each reaction affecting more than 10% of patients (see Investigator's Brochure).

There is a potential risk of local adverse reactions at the administration site following Infudopa, however, local tolerance study in rabbits indicate that this risk should be low, and the reaction only short-term and not severe. However, the interim analysis of 5 patients showed that s.c. administration was associated with hematoma and transient and moderate pain or discomfort. Based on literature data, it was concluded that this was most likely due to the relatively high osmolarity caused by the high citrate concentration of the solution. Thus, when the trial starts again, a new buffer composition named Infudopa Buffer SubC, with a citrate concentration of only 20% of the previous one, will be used for the s.c. administration.

The half-life in plasma is short for levodopa, meaning that a lowering in pump rates following all routes of studied administration will quickly adjust down the levels of levodopa in plasma should, for example, dyskinesia occur. The clinical study is conducted at a phase I centre with intense monitoring of the patients that further reduces the risks. Please also refer to section 6.2 in the clinical study protocol for study dose and study design rationales. Data from the interim analysis have also given information allowing a fine tuning of the dosages.

When the study starts again, there will be a new interim analysis of pharmacokinetics (PK) and safety data after 4 of 18 (or 22 considering also possible compensatory patients) completed patients, after which a monitoring committee will meet to discuss the results and conclude if the study should continue, be modified with respect to design or discontinued. Evaluation will include blood PK samples, inspection of local dermal area/scoring including photos, and adverse events.

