At high concentrations, citrate impairs coagulation. The levels of citrate (as well as those of phosphate) in Infudopa are, however, so low that no significant influence on systemic coagulation

Clinical Study Protocol		Study code:	IPO-001
	linical Study Protocol	Version No:	5.1
C		Date:	26 MARCH
			2019

even at maximal doses is to be expected, and also no other adverse effects of either citrate or phosphate. Nevertheless, safety laboratory analyses have been included in the study to monitor any possible effects on coagulation, by analysing total and ionized calcium and magnesium in serum, and blood base excess.

Hence, relevant precautions have been taken to minimize the risks and discomforts of patients participating in the study. This includes thorough information to the staff at the phase 1 unit where the trial will be conducted regarding the correct administration of the study product and the dose adjustments based on the clinical outcome (dyskinesia or on/off effect) that will aim to mitigate any adverse reactions.

In summary, it may be concluded that the risks for participating PD patients is low, and is outweighed by the profound benefit that a new s.c. and i.v. administration route would present to PD patients. Hence, the risk/benefit ratio for the clinical study is clearly beneficial.

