## 3.3.8. Laboratory Assessments

Blood and urine samples will be taken at the times indicated in the assessment tables (Table 1 and 2). The following samples will be collected and variables measured (see 6.3.2 for total volume):

- Clinical chemistry (calcium, phosphate, total bilirubin, alkaline phosphatase, urea, urate, chloride, creatinine, total protein, albumin, aspartate transaminase (AST), alanine transaminase (ALT), sodium, potassium, creatine kinase (CK), homocysteine, prothrombin complex (PTK-INR), activated partial thromoplasmin time (APTT))
- HIV and hepatit B and C
- Haematology (haemoglobin, platelet count, haematocrit, red blood cell (RBC) count, white blood cell (WBC) count with differentials)
- Total and ionized calcium and magnesium in serum, and blood base excess
- Urinalysis (pH, ketones, glucose, proteins, blood), urine pregnancy test, 10 mL midstream.
- Blood PK samples; Levodopa (LD), carbidopa (CD), and 3-O-methyldopa (3-OMD)

Blood and urine samples (except for PK samples) will be analysed at the site or at the local hospital laboratory according to routine procedures, and then destroyed.

	Study code:	IPO-001
Clinical Study Protocol	Version No:	5.1
	Date:	26 MARCH 2019

Laboratory values outside the reference limits suspected to be of any clinical significance will be re-checked, but without further recording in the eCRF. Subjects in whom the suspected clinical significance is confirmed at the repeated sampling will either not be included or, if already included, will be followed until normalization or for as long as the Investigator considers necessary.

The PK blood samples will be stored at  $-20^{\circ}$ C until shipment to laboratory for analysis.

Details for biological sample handling will be specified in a study specific Laboratory Manual.

Levodopa, carbidopa, and 3-OMD will be analysed at a certified laboratory with Good Laboratory Practice (GLP) standard, and the bioanalytical method should be fully validated according to European Medicines Agency (EMA) Guideline on bioanalytical method validation (July 2011, EMAE/CHMP/EWP/192217/2009). The lower limit of quantification (LLOQ) will be at least 15 ng/mL for plasma of both active ingredients levodopa and carbidopa. Separate bioanalytical study plan will be prepared and approved before study sample analysis.

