# 7. SAFETY

### 7.1. Definitions

## 7.1.1. Adverse event (AE)

An Adverse Event is any untoward medical occurrence in a subject or clinical investigation subject administered a medicinal product and which does not necessarily have a causal relationship with this treatment. An adverse event (AE) can therefore be any unfavourable and unintended sign (including an abnormal laboratory finding), symptom, or disease temporally associated with the use of a medicinal (investigational) product, whether or not related to the medicinal (investigational) product. The terms "infusion site reaction" and "catheter site reaction" are used as predefined skin AE when there is a possible or most likely relation to the locally infused drug or the implanted catheter. More specific terms (like "infusion site pain" or "infusion site erythema") can be used when such symptoms occur in isolation, whereas "reaction" is the preferred description of combinations of symptoms which follow a similar time course.

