## 7.2. Reporting

#### 7.2.1. Adverse event

All AEs occurring during the trial that are observed by the Investigator or reported by the subject, will be recorded by the study personnel on the eCRF, whether or not attributed to trial medication. The following information will be recorded: description, date of onset and end date, severity, assessment of relatedness to trial medication and action taken. Follow-up information should be provided as necessary.

It will be left to the Investigator's clinical judgment to decide whether or not an AE is of sufficient severity to require the participant's removal from treatment. A subject may also voluntarily withdraw from treatment due to what he or she perceives as an intolerable AE. If either of these occurs, the participant must undergo an end of trial assessment and be given appropriate care under medical supervision until symptoms cease, or the condition becomes stable.

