### 8.4. Interim analysis

There has been an interim analysis of first 5 subjects in the study (Clinical Study Interim Report 2019-01-15). There will be a new interim analysis of PK and safety data after 4 completed subjects after the study has re-started. The number of 4 subjects for the interim analysis is because it will allow for reasonably adequate mean values of numerical variables and frequencies of distribution of binominal variables, including reasonable estimates of confidence intervals. The following data will be included in the interim analysis (see Table 1 and 2):

- Blood PK samples
- Inspection of local dermal area/scoring incl. photos
- Adverse events

A Board of the Interim Study Analysis will meet to discuss the results and conclude if the study should continue or not.

The possible outcomes the Board will evaluate, and the basis for the decisions are:

1. Are the plasma levels of LD following s.c. and i.v. too high or too low as compared to Duodopa at any time during the treatment, so a dosage adjustment is necessary? Decision rules:

- If the deviation from Duodopa is of a magnitude that is deemed clinically important, appropriate changes in the dosing protocol in the study will be considered.

- If the deviation from Duodopa at steady-state is larger than established limits for bioequivalence (80% - 125%), the appropriate changes in the dosing protocol will be made.

2. Is the local and systemic tolerance acceptable?

Decision rule:

If adverse events have occurred which, according to the committee, can be attributed to the study drug and make it ethically unjustifiable to pursue the trial, the trial will be stopped. However, the trial can continue after the appropriate changes have been made if it can be convincingly demonstrated that changes in the protocol, e.g. a change of infusion rate, infusion system, an increase in the number of subcutaneous infusion sites or other feasible actions, will mitigate the risk for further adverse events.

In case the dosage regimen is changed, or other major change is made to the Clinical Study Protocol (CSP) an amendment must be submitted to MPA and EC.

Only descriptive summary statistics will be performed. There will be no statistical hypothesis testing.

The members of the Board of the Interim Study Analysis are presented in Appendix C.

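### Repeat results of clinically suspect laboratory values are kept out of the eCRF, and the interim data lists omit laboratory results, so the Board's basis for judging systemic tolerance is incomplete

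*Protocol*

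**What the plan says.** Section 3.3.8 (Laboratory Assessments) sets out what happens when a laboratory value lies outside its reference limits and is suspected to matter clinically. Such values "will be re-checked, but without further recording in the eCRF". Where the repeat sample confirms the suspicion, the subject is either not included or, "if already included, will be followed until normalization or for as long as the Investigator considers necessary". The rule therefore serves eligibility at screening and also operates after dosing.

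Section 6.2 lists laboratory assessments among the secondary variables for safety. Section 1.4 explains why some of them are there: no significant effect of citrate or phosphate is expected, but "safety laboratory analyses have been included in the study to monitor any possible effects on coagulation", by measuring total and ionized calcium, magnesium and base excess.

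On the interim analysis after 4 completed subjects, section 1.4 says: "Evaluation will include blood PK samples, inspection of local dermal area/scoring including photos, and adverse events". Section 8.4 repeats the same three items as bullets. Its second question to the Board of the Interim Study Analysis is: "Is the local and systemic tolerance acceptable"?

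**The concern.** When a post-dose value is out of range, the repeat result does most to separate a real change from a one-off or a laboratory error. The protocol tells the site not to enter that result. This is a stated instruction, not a detail left for a later document. It gives a poorer safety dataset than the one the site already holds.

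The interim lists have a related gap. The trial collects ion and acid-base tests for a systemic concern that section 1.4 itself names. The Board that must judge systemic tolerance is not listed to receive them. The 4 interim subjects are the first to complete after the restart with the changed s.c. buffer, so this is a natural point to look at those values as a group.

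**Working it through.** There is no figure in the plan to reproduce and no calculation behind the point. The check is a comparison of sections.

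1. **Where the repeat result goes.** Section 3.3.8 excludes re-check results from the eCRF. Nothing there excludes the first, scheduled value, so an abnormal first value can sit in the database without the result that confirms or refutes it. Section 9.1.1 keeps laboratory data in source documents, so the result exists and can be monitored. It is not in the data that are locked and analysed under section 9.2.

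2. **Where follow-up values go.** The sentence in 3.3.8 on following confirmed cases gives no recording instruction either way. Their exclusion is not stated, but neither is their entry required.

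3. **How a confirmed abnormality reaches the database.** Section 7.1.1 allows an abnormal laboratory finding to be an adverse event. Section 7.2.1 says "All AEs occurring during the trial that are observed by the Investigator or reported by the subject, will be recorded" on the eCRF, with onset, end date, severity, relatedness and action taken, and with follow-up information as necessary. An abnormality declared an adverse event is therefore documented as an event, but the numbers behind its confirmation and end date are not required in the eCRF. Section 3.3.8 has no cross-reference to 7.2.1, so a site reading it alone is directed to clinical follow-up and not to event recording.

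4. **What the Board is listed to receive.**

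| Data type | Interim list, 1.4 | Interim list, 8.4 |
|---|---|---|
| PK samples | yes | yes |
| Dermal inspection and photos | yes | yes |
| Adverse events | yes | yes |
| Laboratory results | not listed | not listed |

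5. **What the Board must decide.** The question covers local and systemic tolerance. The decision rule attached to it runs on adverse events attributable to the study drug, and those are on the list.

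6. **What falls through.** A laboratory change reaches the Board by the listed route only after an investigator has judged it an adverse event. A shift in the same direction in several of the 4 subjects, each value within limits or judged not significant, would not appear in an event listing. A simple listing of values could show it.

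**The case against.** The strongest reply is that the sections can be followed together. Section 3.3.8 governs entry of re-check results, section 7.2.1 governs entry of adverse events, and nothing in the former waives the latter. A confirmed abnormality recorded as an event has an onset, an end date and follow-up information in the eCRF, and the numeric results stay in source. The interim lists say what will be included and do not say that nothing else may be shown. Section 1.4 expects no significant effect of citrate or phosphate even at maximal doses, and the new s.c. buffer has only 20% of the previous citrate concentration. Part of the re-check rule concerns eligibility, where no post-dose signal exists.

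Most of this stands, and it rules out two stronger readings that a reader might infer. One is that the Board cannot answer its own question on systemic tolerance. The documents do not support that: the decision rule uses adverse events, the Board receives them, and they can include laboratory findings. The other is that confirmation, duration and resolution of an abnormality go unrecorded. That also fails, because 7.2.1 requires this information for anything recorded as an event and 9.1.1 keeps the results in source. Nor does the explicit wording in 3.3.8 imply any motive.

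The reply does not remove the core. Source documents are not the analysis dataset. Permission to show the Board more is not a plan to do so. A precautionary test serves its purpose only if someone reviews the values.

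**Conclusion.** The point holds as a gap in data capture and interim reporting. By explicit instruction, the numeric repeat results for clinically suspect laboratory values, including those after dosing, stay outside the analysis database even though laboratory assessments are a secondary safety variable. Both interim data lists omit laboratory results, so the Board's view of systemic tolerance depends on investigators having already declared laboratory changes as adverse events. That basis is incomplete, not absent.

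The size cannot be put as a rate, because the protocol gives no frequency of out-of-range values, re-checks or laboratory adverse events. The scope is every re-check result and, at the interim, the laboratory data of 4 subjects. The conclusion assumes that sites follow 3.3.8 as written and that the Board receives what 1.4 and 8.4 list and no more. If laboratory listings are in practice supplied, the interim half of the point reduces to a wording change. The change is worth making because it is cheap, but the point does not call the trial's primary conclusions into question.

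**What to change.** - **Section 3.3.8:** delete the clause that keeps re-checks out of the eCRF. State that repeat and follow-up values for included subjects are entered as dated unscheduled laboratory results. Add a cross-reference to adverse-event recording in 7.2.1; this makes an existing duty visible and does not create a new one.
- **Sections 1.4 and 8.4:** add to the interim data a descriptive listing of the laboratory results already collected, including total and ionized calcium, magnesium and base excess. This fits the statement in 8.4 that the interim is descriptive and involves no hypothesis test.

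The cost is one unscheduled-laboratory page in the eCRF, the entry work for repeat values, and one extra interim listing. No additional sampling is needed, and clinical follow-up of subjects is unchanged.

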#### 3.3.9. Video recordings

Each of the video sequences to be recorded on Day 1 will contain the following tasks: finger tapping, leg agility, alternating hand movements, arising from a chair, and walking (at least 3 m). Assessments of the video sequences will be made by two senior neurologists after the study. The order of the recordings will be randomized between time, subjects and treatments. All video recordings will be installed on two laptop computers together with a rating form for the items described below. The assessors will be trained before the study, using video recordings from previous studies. The order of the video sequences will be broken when all assessments are finalized.

The operational definitions of the motor examination part of the Unified Parkinson's Disease Rating Scale (UPDRS) (Fahn et al, 1987) will be used for finger tapping (item 23), rapid alternating movements of hands (item 25), leg agility (item 26), arising from chair (item 27), gait (item 29), and bradykinesia (item 31). These items are considered to be the most relevant and convenient for the brief recordings. Dyskinesias will be observed on the video recordings, and reported using the definitions of the Modified Dyskinesia Scale (Goetz et al. 1994).

A Treatment Response Scale (TRS) (Nyholm et al, 2005) will be used for a global assessment of clinical response. The TRS ranges from -3 (severe "off") to +3 ("on" with severe dyskinesia), where 0 is "on" without any dyskinesias.

A composite secondary efficacy variable will be the percentage of TRS ratings within the interval -1 to +2 that is, a clinically desirable, functional "on" state accepting mild parkinsonism and not more than moderate dyskinesia, and percentage of ratings within the intervals -3 to -2 (severe to moderate "off") and +3 ("on" with severe dyskinesia). Interrater reliability will be assessed using percentage agreement between the raters and  $\kappa$  (kappa) coefficients. Kappa coefficients between 0.60 and 0.80 are considered "good" and coefficients higher than 0.80 "very good."

## 3.3.10. Parkinson's KinetiGraph

Parkinson Kinetigraph recordings will be obtained from the wrist on the subjects most disease affected side. Recordings will start in the morning of day 1 of each treatment visit and continue for up to 24h or until the subject leaves the trial site on day 2. The accelerometer data will be uploaded and proprietary algorithms (Global Kinetics Corporation, Melbourne, Australia) will be used to calculate the 25th, 50th and 75th percentiles of a bradykinesia score (BK) and a dyskinesia score (DK) over the time-period 09-18 as well as +1h to +16h from pump start. Tremor episodes consisting of at least 10 seconds meeting the operational tremor criteria defined by Braybrook et al (2016) will be recorded and the percent of time with ongoing tremor between 9-18 as well as +1h to +16h after pump start will be calculated. The interquartile ranges of BK and DK will be used to calculate a fluctuation score (FDS) for the measured time periods. Other outcomes will be median BK, DK, FDS scores as well as percent time with tremor in the normal daytime period (9-18) as well as the entire infusion period following the first hour after treatment start.

## 4. STUDY POPULATION

Each patient should meet all of the inclusion criteria and none of the exclusion criteria for this study. Under no circumstances can there be exceptions to this rule.

## 4.1. Inclusion criteria

For inclusion in the study, patients should fulfill the following criteria:

- 1. Signed informed consent
- 2. Male or female patients at least 30 years old
- 3. Patients with advanced Parkinson's disease who are already on LCIG (Duodopa®) for at least 30 days, on a stable treatment regimen of 600 mg to 4000 mg levodopa per day, and with approximately 16- or 24-h Duodopa infusion regimens
- 4. Patients with a Hoehn and Yahr (H&Y) score of ≤ 3 on Duodopa treatment (including concomitant medication)
- 5. Body mass index range from 18.0 to 35.0 kg/m^2
- 6. Patients in general good health, as judged by the Investigator, and as determined by vital signs, medical history, physical examination, ECG, and laboratory tests
- 7. Females of childbearing potential must have a negative pregnancy test prior to randomization and must be willing to use a highly effective contraceptive measure during relevant systemic exposure to the investigational drug and the first menstrual cycle after treatment cessation (see section 7.3).
- 8. Males must be willing to refrain from fathering a child, including sperm donation, during the study and 3 months following the last dose.

## 4.2. Exclusion criteria

Patients must not enter the study if any of the following criteria are fulfilled:

- 1. Simultaneous participation in any other clinical drug trial
- 2. Clinically significant abnormal laboratory data at baseline or any abnormal laboratory value that could interfere with the study assessments

- 3. Patients with current serious symptomatic CNS-lesions, neurological, psychiatric, or behavioral disorders other than Parkinson's disease (e.g. major stroke, epilepsy, substance use disorder, previous neurosurgery including DBS) and that may interfere with the conduct or interpretation of the study
- 4. History or presence of any condition that can interfere with absorption, distribution, metabolism, or excretion of study drug (not including the percutaneous endoscopic gastrojejunostomy tube needed for Duodopa administration)
- 5. Patients on medication with warfarin, dabigatran, rivaroxaban, apixaban, edoxaban, monoamine oxidase-A inhibitors and alpha-methyldopa (within the last 60 days); selegiline, catechol-O-methyltransferase (COMT) inhibitors other than a single daily dose of entacaponeparenteral ergots, anticholinergics, methylphenidate, amphetamine, isoprenaline, adrenaline, dobutamide, reserpine, or other drugs with known dopamine receptor antagonistic effect (within the last 30 days); and iron salts (within the last 7 days), or any other treatment that could affect the metabolism of levodopa
- 6. Patients who use antineoplastic chemotherapy or biological immunosuppressants (within the last 5 years), and drugs known to increase risks for cardiac toxicity, Torsade de Pointes, sudden death or prolonged QT interval (within five elimination half-lives before baseline and for the duration of the study)

